5 EFFECTIVENESS ANALYSIS STRATEGY

For analysis of refractive outcomes, the spherical component of the manifest and cycloplegic refractions (as tested at 4.0 m) will be adjusted for optical infinity by adding -0.25 D to the spherical magnitude for all post-operative assessments. Similarly, manifest refraction

spherical equivalent (MRSE) will be calculated using the respective adjusted manifest and cycloplegic sphere values.

Unless otherwise specified, MRSE will be based on the subject's manifest refraction, not on the value collected by the sightmap device (measured refraction). Additionally, all visual acuity categories will be determined using logMAR values.

For analyses involving visual acuity, Snellen lines will be based on the conversion from logMAR line ± 2 letters (e.g., 20/20 Snellen = -0.04 to 0.04 logMAR).

Note: Effectiveness analyses based on FAS or CC excludes all data/subjects that have met any of the Data Set Analysis Restrictions (DSARs) identified in the Deviation and Evaluability Plan (DEP).

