10.2.3 Best Corrected Distance Visual Acuity

Visit 0, Visit 2/2A – 7/7A, Early Exit

Perform best corrected visual acuity testing with the Sponsor provided electronic visual acuity system for both eyes prior to any assessment requiring administration of eye drops to dilate the eyes, or any assessment requiring contact with the eye. The system for this study is M&S Technologies' Clinical Trial Suite (CTS). The CTS is comprised of a 13-inch laptop computer and a control tablet. Background luminance is standardized and automatically calibrates to study specifications (approximately 85 cd/m² for photopic lighting conditions). VA optotypes are calibrated for both distance-to-subject and pixels-per-inch. The testing distance for this assessment is 4m. Visual acuity must be obtained by study personnel who have successfully completed required training to conduct the assessment.

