10.2.5 Cycloplegic Refraction

Visit 0, Visit 5/5A

Perform the cycloplegic refraction after instilling cycloplegic drops using your standard of care method.

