10.2.13 Manifest Refraction / Subjective Refraction

Visit 0, Visit 2/2A - 7/7A, Early Exit

Perform manifest refraction under photopic lighting conditions and measure vertex distance using a phoropter.

Note: The chart used for subjective Manifest Refractions can depend on use of the data:

- For Inclusion stability at Screening (Visit 0) performed on site chart
- For VA testing performed on Sponsor provided electronic chart
- See MOP for more details.

Note: Refraction for Inclusion Criteria 4 for myopic and astigmatic range must come from the InnovEyes sightmap Measured refraction.

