1.2 Study Description

This is a prospective, single-arm, multi-center, interventional study with planned bilateral InnovEyes LASIK treatment for subjects requiring refractive correction of myopia with or without astigmatism. All treated eyes will be targeted for emmetropia based upon the InnovEyes sightmap Measured Refraction. The postoperative state of each treated eye will be compared to the preoperative state of the same eye.

Subjects will be evaluated initially for suitability as candidates for bilateral LASIK. Potential subjects willing to participate will be consented and screened. Approximately 187 qualified subjects (up to 374 eyes) will receive bilateral InnovEyes LASIK and be followed for 1 year. Total duration of subject participation is approximately 1 year and includes 9 study visits consisting of Screening, Surgery, 1 day, 1 week, 1 month, 3 month, 6 months, 9 months, and 12 months. Subjects will be enrolled with intent to treat at least 20 eyes in each spherical diopter and each cylindrical diopter range (with only 10 eyes in the highest cylinder bin). Approximately 10 US study sites will participate in this clinical study. It is estimated that enrollment and follow-up of all subjects will take approximately 22 months.

The schedule of study procedures and assessments can be found in Section 10, Appendix – Schedule of Study Procedures and Assessments.

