4 REFRACTIVE STABILITY

Stability analyses will be performed on eyes that have every follow-up exam from 1-month up to the stability time point (the CC), as well as on the eyes that have 2 consecutive exams, but not necessarily every follow-up exam. The following stability analyses will be performed for the time intervals between all consecutive pairs of scheduled postoperative refractions:

- Percentage of eyes that achieve:
 - o a change of less than or equal to 1.00 D of MRSE between two refractions performed at 1 month and 3 months, and between subsequent refractions performed at least 3 months apart;
 - o a change of less than or equal to 0.50 D of MRSE between two refractions performed at 1 month and 3 months, and between subsequent refractions performed at least 3 months apart;
- Mean overall change and change per month in MRSE between consecutive scheduled visits as determined by a paired analysis;
- Mean \pm SD MRSE for the preoperative and each postoperative visit;
- Assessment of cylinder stability for correction of spherocylindrical refractive errors;

Refractive stability is achieved at the latter of two postoperative manifest refractions performed at least 3 months apart or at 3 months after surgery when compared with the 1-month interval, when all of the following recommended criteria are met:

- At least 95% of the treated eyes have a change ≤ 1.00 D of MRSE between the 2 refractions;
- The mean rate of change in MRSE, as determined by a paired analysis, is ≤ 0.5 D per year (0.04 D/month) over the same time period;
- The mean rate of change of MRSE decreases monotonically over time, with a projected asymptote of zero or a rate of change attributable to normal aging;
- The 95% confidence interval for the mean rate of change in MRSE includes zero or a rate of change attributable to normal aging; and
- Stability is confirmed at least 3 months after the stability time point by a statistically adequate subgroup (at least 80% of the cohort).

The primary safety and effectiveness endpoints for the study can only be evaluated once refractive stability has been established within the CC, as well as on the eyes that had 2 consecutive exams, but not necessarily every follow-up exam.

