6 SAFETY ANALYSIS STRATEGY

All adverse events occurring from the time a subject signs informed consent to study exit will be accounted for in the reporting. Safety analyses will be conducted using the SAF through descriptive summaries (counts and percentages) and listings. In addition, separate subject listings will be provided for AEs that occur in subjects:

• after signing informed consent but prior to exposure to IP (InnovEyes sightmap)

• exposed to IP (InnovEyes sightmap) but do not proceed to InnovEyes treatment (and thus are not included in the SAF)

Note: For analysis of refractive outcomes, the spherical component of the manifest and cycloplegic refractions (as tested at 4.0 m) will be adjusted for optical infinity by adding -0.25 D to the spherical magnitude for all post-operative assessments. Similarly, manifest refraction spherical equivalent (MRSE) will be calculated using the respective adjusted manifest and cycloplegic sphere values.

Unless otherwise specified, MRSE will be based on the subject's manifest refraction, not on the value collected by the sightmap device (measured refraction). Additionally, all visual acuity categories will be determined using logMAR values.

For analyses involving visual acuity, Snellen lines will be based on the conversion from logMAR line ± 2 letters (e.g., 20/20 Snellen = -0.04 to 0.04 logMAR).

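### The SAP corrects sphere for the 4 m test distance only after surgery and assumes 4 m for cycloplegic refraction, so pre/post MRSE summaries may carry an artefact of up to 0.25 D

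*SAP*

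**What the plan says.** SAP section 5 takes the sphere of both manifest and cycloplegic refractions, treats both as done at 4.0 m, and states that it "will be adjusted for optical infinity by adding -0.25 D to the spherical magnitude for all post-operative assessments". The note in SAP section 6 repeats the rule: "adjusted for optical infinity by adding -0.25 D to the spherical magnitude for all post-operative assessments". MRSE is then computed from the adjusted sphere. No adjustment of a preoperative value appears in the legible text.

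The protocol describes the refractions as follows:

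- **Manifest (10.2.13, and footnote 7 of Table 3–1).** There are two kinds of refraction at Visit 0. The one used to show stability for inclusion is on the site's own chart. The other is described as "For VA testing performed on Sponsor provided electronic chart".
- **Sponsor chart distance (10.2.3, covering Visit 0 and Visits 2 to 7).** "The testing distance for this assessment is 4m".
- **Cycloplegic (10.2.5, Visits 0 and 5).** "Perform the cycloplegic refraction after instilling cycloplegic drops using your standard of care method". Section 10.1 also lets cycloplegic data from a routine LASIK evaluation serve as screening data.

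On use, SAP section 4 lists mean and SD "MRSE for the preoperative and each postoperative visit", and SAP section 1.2 says: "The postoperative state of each treated eye will be compared to the preoperative state of the same eye".

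**The concern.** A finite test distance adds plus power to the refraction that depends on the lane and not on whether the eye has been operated on. If the Visit 0 value and the later values come from the same 4 m chart and only the later ones are corrected, the two columns of the SAP 4 summary are on different scales. Part of the difference between them is then not a treatment effect.

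For cycloplegic refraction the rule rests on a distance that the protocol text does not set. A site that refracts in a longer lane would have its Visit 5 values moved further towards myopia than the optics require.

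At stake is the accuracy of descriptive pre/post refractive summaries in a study that may support a Pre-Market Approval application (Protocol 7.1). The pass/fail rules are not at stake, as the working shows.

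**Working it through.** **Inputs.** The adjustment is -0.25 D, postoperative only, with an assumed distance of 4.0 m (SAP 5 and 6). The sponsor chart distance is 4 m (Protocol 10.2.3). The site-chart and cycloplegic distances are not stated, so 5 m, 6 m and optical infinity are used below as assumptions.

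**Step 1: the plan's own figure.** Vergence at distance d is 1/d. At 4.0 m, 1/4.0 = 0.25 D. The stated correction is exactly right for a 4 m test.

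**Step 2: pre/post difference as the rule stands.** Let s be the true sphere at infinity. A refraction at distance d reads s + 1/d.

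- Preoperative, uncorrected: s_pre + 1/d_pre
- Postoperative at 4 m, corrected: s_post + 0.25 - 0.25 = s_post
- Difference: (s_post - s_pre) - 1/d_pre

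The artefact is therefore -1/d_pre. The preoperative eye looks less myopic than it was, and the correction achieved looks smaller than it was.

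**Step 3: cycloplegic value at Visit 5.** A refraction at distance d that receives -0.25 D is shifted by -(0.25 - 1/d) relative to its true value.

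| Test distance | Pre/post artefact, -1/d_pre | Visit 5 cycloplegic error, -(0.25 - 1/d) |
|---|---|---|
| 4 m | -0.25 D | 0 D |
| 5 m (assumed) | -0.20 D | -0.05 D |
| 6 m (assumed) | -0.17 D | -0.08 D |
| Infinity (assumed) | 0 D | -0.25 D |

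The pre/post column applies to whichever Visit 0 manifest refraction is used as baseline. The legible SAP does not say which that is.

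**Step 4: what the rule does to the decision criteria, with signed sphere.**

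- *MRSE within 0.50 D and within 1.00 D.* These use the postoperative manifest refraction only. At 4 m, -0.25 D is the correct adjustment, so there is no bias.
- *Refractive stability.* All changes are between two postoperative visits: (a - 0.25) - (b - 0.25) = a - b. In a check on 374 simulated eyes the shift altered no interval change (largest discrepancy about 2e-16 D) and left the share of changes within 1.00 D identical.
- *Increase in astigmatism above 2.00 D.* This is the one co-primary endpoint that compares with the preoperative refraction, and it uses cylinder, which is not adjusted.
- *UCDVA, BCDVA and serious ocular adverse events.* None of these uses sphere.

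**The case against.** The strongest reply is that nothing decisive depends on this. The only legible pre/post use of MRSE is one descriptive line in SAP 4, and SAP 1.2 is a general statement of design that specifies no MRSE-change analysis. The -0.25 D artefact is a maximum. If the baseline is the site-chart refraction in a lane calibrated for infinity, it is zero, and a postoperative-only rule might then be deliberate. The phrase about 4.0 m may restrict the rule to refractions at that distance, and the Manual of Procedures, which holds the procedural detail (Protocol 10.2), may fix the cycloplegic distance. Against a treatment range to -11.00 D, 0.25 D is small in a mean.

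Most of this stands, and it limits the point to descriptive summaries. It does not remove the point. The protocol puts a Visit 0 refraction on the same sponsor chart, the SAP does not say which Visit 0 refraction is baseline, and the legible protocol gives no basis for 4.0 m under cycloplegia. If the phrase is a restriction, the SAP gives no rule for other distances.

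A reader might also infer that the word magnitude in the rule inflates the MRSE co-primary endpoints. Taken literally, it would turn a sphere of -0.50 D into -0.25 D, where correction to infinity needs -0.75 D. In a simulation of 400,000 spherical eyes (assumed SD 0.45 D, values rounded to 0.25 D), the share within 0.50 D would then be about 91% instead of 84% for a true mean of 0, and about 95% instead of 77% for a true mean of -0.25 D. The documents do not support that reading. The stated purpose is adjustment to optical infinity, which adding a negative number achieves only on signed sphere, and the next sentence builds MRSE from adjusted sphere values, not absolute ones. Under the assumed distributions both readings also clear the 50% target. It is loose wording to tidy, not evidence of a wrong calculation.

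**Conclusion.** The point holds for preoperative versus postoperative sphere and MRSE summaries, which may carry an artefact of 0 to -0.25 D. The full -0.25 D applies if baseline is the 4 m sponsor-chart refraction. Visit 5 cycloplegic values may separately be over-corrected by 0 to 0.25 D, depending on a lane distance that the documents do not give.

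Two wider readings are tempting and not supported. One is that the asymmetry biases the co-primary endpoints or the stability decision: with signed sphere it affects neither. The other is that it distorts a planned comparison of cycloplegic with manifest refraction at month 6: no such analysis appears in the legible SAP, although parts of it cannot be read.

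The conclusion assumes that the sponsor-chart refraction is done at the 4 m used for acuity on that chart, as the SAP itself takes it to be, and that no preoperative adjustment is specified in text that is not legible.

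**What to change.** In SAP 5 and 6, replace the adjustment sentence with a rule based on test distance:

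- Apply the correction to the signed sphere (dropping the word magnitude) of every refraction, preoperative and postoperative: -0.25 D at 4 m, -1/d D at any other distance d in metres, and none where the lane is calibrated for infinity.
- Name the Visit 0 sponsor-chart refraction as the preoperative MRSE in all pre/post summaries.
- Apply the correction to cycloplegic refractions only where the test distance is documented, citing the Manual of Procedures if it sets one.

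The cost is SAP wording and one query per site on lane distance. No new patient measurements are needed. Postoperative manifest values at 4 m do not change, so the co-primary results stay as they are. The visible effect is a preoperative mean MRSE up to 0.25 D more myopic.

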5.1 Analysis of Primary Effectiveness Endpoints

In order to establish effectiveness of the WaveLight EX500 excimer laser system for the correction of myopia with and without astigmatism using InnovEyes in conjunction with InnovEyes sightmap, the following four co-primary endpoints are defined:

- Percentage of eyes with UCDVA of 20/40 or better (in eyes with preoperative BCDVA of 20/20 or better) at refractive stability (Target: ≥ 85%)
- Percentage of eyes with MRSE within 0.50 D at refractive stability (Target: $\geq 50\%$)
- Percentage of eyes with MRSE within 1.00 D at refractive stability (Target: $\geq 75\%$)
- Percentage of eyes that achieve refractive stability (Target: $\geq 95\%$)

5.1.1 Statistical Hypotheses

[figure not shown]
No hypothesis testing of the primary effectiveness endpoints is planned.

5.1.2 Analysis Methods

[figure not shown]
The FAS will be used for this analysis. The number and percentage of eyes meeting each of the primary effectiveness endpoints will be calculated. The effectiveness criteria will be considered to have been met if the percentage meets or exceeds the target rate at the time of refractive stability for all primary effectiveness endpoints. These analyses will be performed for the whole FAS

An analysis will be performed once refractive stability is achieved; a final summary of these endpoints will be performed once the one year follow up is complete.

Document ID: Status: Approved, Version: 4.0 V-CLN-0000922 Approved Date: 30 Nov 2022

[figure not shown]

[figure not shown]

[figure not shown]

[figure not shown]

[figure not shown]
Document ID:

6 SAFETY ANALYSIS STRATEGY

All adverse events occurring from the time a subject signs informed consent to study exit will be accounted for in the reporting. Safety analyses will be conducted using the SAF through descriptive summaries (counts and percentages) and listings. In addition, separate subject listings will be provided for AEs that occur in subjects:

• after signing informed consent but prior to exposure to IP (InnovEyes sightmap)

• exposed to IP (InnovEyes sightmap) but do not proceed to InnovEyes treatment (and thus are not included in the SAF)

Note: For analysis of refractive outcomes, the spherical component of the manifest and cycloplegic refractions (as tested at 4.0 m) will be adjusted for optical infinity by adding -0.25 D to the spherical magnitude for all post-operative assessments. Similarly, manifest refraction spherical equivalent (MRSE) will be calculated using the respective adjusted manifest and cycloplegic sphere values.

Unless otherwise specified, MRSE will be based on the subject's manifest refraction, not on the value collected by the sightmap device (measured refraction). Additionally, all visual acuity categories will be determined using logMAR values.

For analyses involving visual acuity, Snellen lines will be based on the conversion from logMAR line ± 2 letters (e.g., 20/20 Snellen = -0.04 to 0.04 logMAR).

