Study Design	This is a prospective, single-arm, multi-center, interventional study with planned bilateral treatment. Qualified subjects will receive bilateral InnovEyes treatment and be followed for 1 year. Subjects will be asked to attend a total of 9 visits (screening, surgery, day 1, 1 week, 1 month, 3 month, 6 month, 9 month, and 1 year). Total expected duration of subject participation is approximately 1 year.
Subject Population	Subjects who desire to have LASIK will be consented and screened for meeting the inclusion and exclusion criteria. Subject enrollment will be monitored to ensure inclusion of required numbers of subjects in each one diopter interval based on the ranges of spherical and cylindrical refractive error (bin).
Key Inclusion Criteria (See Section 8.1 for a complete list of inclusion criteria)	 Subjects must meet all inclusion criteria as listed in Section 8.1 Key Inclusion Criteria include: Myopia up to and including -11.00 D with or without astigmatism up to -4.50 D, with spherical equivalent no more than -12.00 D as shown from InnovEyes sightmap Measured refraction Best corrected photopic distance visual acuity of 20/20 or better (≤ 0.04 logMAR) Uncorrected photopic distance visual acuity of 20/40 or worse (≥ 0.34 logMAR) Stable refraction (within ± 0.50 D) as determined by MRSE for a minimum of 12 months prior to surgery
Key Exclusion Criteria (See Section 8.2 for a complete list of exclusion criteria)	 Subjects must not meet exclusion criteria as listed in Section 8.2 Key Exclusion Criteria include: History or evidence of active or inactive corneal disease or retinal vascular disease, keratoconus or glaucoma (or suspect) Previous intraocular or corneal surgery Intent to have monovision treatment
Data Analysis and Sample Size Justification	The safety analysis set (SAF) will contain all eyes that undergo surgery or attempted surgery (defined as eye drops given for flap treatment); the SAF will be the primary analysis set for the safety

analyses. The full analysis set (FAS) will contain all eyes that successfully undergo surgery; the FAS will be the primary analysis set for the effectiveness analyses. The consistent cohort (CC) will contain all eyes in the FAS that have manifest refraction data at all post-operative visits. The CC will be the primary analysis set for the refractive stability analyses.

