8 STUDY POPULATION

The study population consists of subjects who desire to have and qualify for LASIK treatment, are 18 years of age or older, and have myopia up to -11.00 D with or without astigmatism up to -4.50 D. This study is aimed to enroll (consent) approximately 374 subjects at up to 10 sites in the United States with a target of up to 374 eyes treated. Because about 50% screening failure rate and up to 10% lost to follow-up rate is expected, these numbers will allow for treatment and follow-up of at least 300 eyes and account for overlap or overenrollment in certain ranges to achieve the required number of 20 eyes per diopter over the intended refractive range. Allocation of study bins will be closely monitored through the use of listings generated from the InnovEyes sightmap Measured refraction entered in EDC. Investigative sites will be trained on the importance of timely entry of data in EDC to ensure enrollment bin allocation is up to date. When enrollment in a refractive bin is complete, sites will be instructed to refrain from enrolling eyes in that bin. Site-specific targets may vary based upon individual site capabilities, but each site is expected to treat a minimum of 20 eyes and no more than 92 eyes per site.

Enrollment will be monitored to aim for 20 or more eyes treated and followed to refractive stability in each diopter interval based on the ranges of spherical and cylindrical refractive error (bin). Therefore at least 220 eyes will be treated for the sphere range (20 eyes/diopter interval of 0 to -11.00) and at least 110 eyes will be treated for the cylinder range (20 eyes for 0 to \leq -0.50 and > -0.50 to \leq -1.00 cylinder and 20 eyes/diopter for intervals from > -1.00 to

-4.00 and 10 eyes in > -4.00 to -4.50). For a diagram showing the study bins, refer to the Manual of Procedures (MOP). All bin assignments are made based on the InnovEyes sightmap Measured refraction entered in EDC. Estimated time needed to recruit subjects for the study is approximately 10 months; however, unanticipated circumstances may shorten or lengthen this time and would not require amendment of this protocol.

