11 ADVERSE EVENTS AND DEVICE DEFICIENCIES

11.1 General Information

An AE is any untoward medical occurrence, unintended disease or injury, or untoward clinical signs (including abnormal laboratory findings) in subjects, users, or other persons, whether or not related to the investigational medical device (test product). Refer to the Glossary of Terms and figures below for categories of AEs and SAEs.

Figure 11–1 Categorization of All Adverse Events

[figure not shown]
[figure not shown]

Figure 11–2 Categorization of All Serious Adverse Events

Specific Events Relevant to this Protocol

In addition to reporting all AEs (serious and non-serious) meeting the definitions, the Investigator must report any occurrence of the following as an ocular SAE:

- Diffuse lamellar keratitis (Grade 3 or above)
- Corneal infiltrate or ulcer
- Any persistent corneal epithelial defect at one month or later
- Corneal edema at 1 month or later (specify flap or bed)
- Epithelium in the interface with loss of 2 lines (10 letters) or more BCDVA

- Miscreated flap (lost, incomplete, too thin)
- Melting of the flap
- IOP with increase of > 10 mmHg above baseline on two consecutive examinations or an IOP greater than 30 mmHg on two consecutive examinations
- Haze beyond 6 months with loss of 2 lines or greater (≥ 10 letters ETDRS) of BCDVA
- Decrease in BCDVA of greater than or equal to 2 lines (≥ 10 letters ETDRS) not due to irregular astigmatism as shown by rigid contact lens refraction at 3 months or later
- Retinal detachment
- Retinal vascular accidents
- Ocular penetration
- Any other vision-threatening event

The Investigator must also report the following ocular AEs:

- Diffuse lamellar keratitis (Grade 2 or less)
- Corneal edema between one week and 1 month after the procedure
- Peripheral corneal epithelial defect at 1 month or later (location of the defect to be identified as on, off, or across the flap)
- Epithelium in the interface
- Foreign body sensation at 1 month or later
- Pain at 1 month or later
- Ghost/double images in the operative eye
- Flap is not of the size and shape as initially intended or microkeratome stopped in midcut or resultant flap is misaligned

AEs that occur in association with a device that is used in conjunction with the FS200 laser system will be reported separately from those occurring with the EX500 laser or sightmap.

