6.1 Analysis of Primary Safety Endpoints

In order to establish safety of the WaveLight EX500 excimer laser system for the correction of myopia with and without astigmatism using InnovEyes in conjunction with InnovEyes sightmap, the following four co-primary endpoints are defined:

- Percentage of eyes that lose 2 lines or more of BCDVA (Target at refractive stability ≤ 5%)
- Percentage of eyes with BCDVA worse than 20/40 (for eyes with BCDVA of 20/20 or better pre-op) (Target at refractive stability ≤ 1%)
- Percentage of eyes that have an increase of manifest refractive astigmatism of greater than 2.00 D of absolute cylinder as compared to the preoperative refraction (Target at refractive stability $\leq 5\%$)
- Percentage of eyes with a serious, non-flap related, ocular adverse event at the postoperative visits (Target per event type at refractive stability: ≤ 1%)

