6.1.2 Analysis Methods

The SAF will be used for this analysis. The number and percentage of eyes experiencing each of the primary safety endpoints will also be calculated. The safety criteria will be considered to have been met if the percentage is less than the target rate at the time of refractive stability

for all of the primary safety endpoints. Adverse events that are non-flap related will be indicated as such on the adverse event CRF. It should be noted that the percentage of eyes with a serious, non-flap related, ocular adverse event will be compared to the 1% target by adverse event type (not for all ocular adverse event types combined).

[figure not shown]
Summary statistics for the primary safety endpoints will be presented by site, race and ethnicity, age (> 21 years old vs. \leq 21 years old), and by gender.

[figure not shown]

[figure not shown]
Document ID: V-CLN-0000922

Page 25 of 56

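### Does the SAP's ±2-letter Snellen conversion let losses of 6 to 9 letters count as a 2-line loss of BCDVA?

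*SAP*

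**What the plan says.** SAP section 6 (Safety Analysis Strategy), like section 5, sets a conversion: "For analyses involving visual acuity, Snellen lines will be based on the conversion from logMAR line ± 2 letters". Its one example assigns 20/20 to the range -0.04 to 0.04 logMAR. The sentence before it says that acuity categories are determined from logMAR values.

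SAP 6.1 lists the co-primary in question, with its target in per cent: "Percentage of eyes that lose 2 lines or more of BCDVA (Target at refractive stability ≤ 5". Neither SAP 6.1 and 6.1.2 nor Protocol 6.3.1 and 12.7.1 attach a letter or logMAR threshold to it. SAP 6.1.1 plans no hypothesis test, and SAP 6.1.2 sets the decision rule: "The safety criteria will be considered to have been met if the percentage is less than the target rate".

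Protocol 11.1 gives a 2-line loss of BCDVA a number in three of its ocular SAE definitions:

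- for a fall in acuity in its own right, "Decrease in BCDVA of greater than or equal to 2 lines (≥ 10 letters ETDRS) not due to irregular astigmatism";
- for epithelial ingrowth, "Epithelium in the interface with loss of 2 lines (10 letters) or more BCDVA";
- for late corneal haze, "Haze beyond 6 months with loss of 2 lines or greater (≥ 10 letters ETDRS) of BCDVA".

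The Protocol Summary sets the entry limit: "Best corrected photopic distance visual acuity of 20/20 or better (≤ 0.04 logMAR".

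**The concern.** The conversion is worded to cover analyses involving visual acuity in general, and it comes just before a co-primary that counts lines. Taken literally, each eye is placed in a 5-letter bin before and after surgery, and lines lost are the number of bins crossed. An eye that enters at the worst letter of the 20/20 bin could then be scored as losing two lines after a loss of only 6 letters. A larger loss of 9 letters from the best letter of the same bin would score as one line.

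The co-primary is judged on its observed percentage alone, in an open-label single-arm study, so the counting rule feeds straight into a success criterion. If the rule were left open, the choice could be made after the data were seen. The report might also carry a co-primary count of 2-line losses based on bins beside SAE counts based on 10 letters.

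**Working it through.** **Inputs.** The bin width comes from SAP section 6, the entry limit from the Protocol Summary, and the 10-letter equivalence from Protocol 11.1. The numbers of eyes are 374 (the maximum treated, SAP section 7) and 300 (Protocol section 8: "these numbers will allow for treatment and follow-up of at least 300 eyes"). The documents give no SD for the pre-to-post change in letters, so SD is varied as an assumption.

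**The SAP's own example.** Two letters are 0.04 logMAR, so one letter is 0.02. Then 0.00 ± 2 × 0.02 gives -0.04 to 0.04, as stated. The next two bins are 0.06 to 0.14 and 0.16 to 0.24.

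**Two eyes under the bin reading.**

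- From 0.04 to 0.16: 0.12 / 0.02 = 6 letters, two bins crossed, counted.
- From -0.04 to 0.14: 0.18 / 0.02 = 9 letters, one bin crossed, not counted.

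**General rule.** Let a be the starting position within the bin in letters (-2 to 2, with 2 the worst) and L the letters lost. Lines lost = floor((a + L + 2) / 5). Two or more lines requires a + L + 2 ≥ 10, that is L ≥ 8 - a. The threshold is therefore 10 letters at a = -2, 8 at a = 0 and 6 at a = 2.

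| Letters lost | Starting positions that count | Share |
|---|---|---|
| 5 or fewer | 0 of 5 | 0 |
| 6 | 1 of 5 | 0.2 |
| 7 | 2 of 5 | 0.4 |
| 8 | 3 of 5 | 0.6 |
| 9 | 4 of 5 | 0.8 |
| 10 or more | 5 of 5 | 1.0 |

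This step needs no distributional assumption. Bins never miss a loss of 10 letters; they can only add eyes.

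**Rates.** Assume the letter change is normal with mean 0, rounded to whole letters, and that a is uniform. Then:

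- letter rate = P(L ≥ 10)
- bin rate = P(L ≥ 10) + 0.2 P(L = 6) + 0.4 P(L = 7) + 0.6 P(L = 8) + 0.8 P(L = 9)

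At SD 5 the bin rate is 0.0287 + 0.2(0.0389) + 0.4(0.0300) + 0.6(0.0222) + 0.8(0.0158) = 0.0745.

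| Assumed SD (letters) | Bin rate | Letter rate | Expected eyes of 300 | Expected eyes of 374 |
|---|---|---|---|---|
| 3.5 | 2.33% | 0.33% | 7.0 v 1.0 | 8.7 v 1.2 |
| 4 | 3.85% | 0.88% | 11.6 v 2.6 | 14.4 v 3.3 |
| 4.5 | 5.59% | 1.74% | 16.8 v 5.2 | 20.9 v 6.5 |
| 5 | 7.45% | 2.87% | 22.4 v 8.6 | 27.9 v 10.7 |

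The bin rate reaches 5% at an SD of 4.33 letters, where the letter rate is 1.4%. The letter rate reaches 5% only at 5.78. With a mean gain of 1 letter, SD 3.5 gives 1.2% v 0.1% and SD 5 gives 5.1% v 1.8%.

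**Sensitivity to starting position.** At SD 5 and mean 0, the bin rate is P(L ≥ 10) = 2.9% if every eye starts at the best letter of its bin, P(L ≥ 8) = 6.7% at the centre and P(L ≥ 6) = 13.6% at the worst letter. The 7.45% is an average over the five positions.

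**Which reading the text supports.** The conversion already has a full job as a category rule. It fixes the 20/40 cuts in the UCDVA co-primary and in the BCDVA co-primary for eyes worse than 20/40, and it matches the 0.04 logMAR limit for 20/20 at entry. Nothing visible extends it to change scores. Wherever the protocol gives a 2-line BCDVA loss a number, the number is 10 letters.

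**The case for a change.** The strongest case for a change is that the bin is the only definition of a line in the visible SAP, that its wording is not confined to categories, and that one sentence would settle a criterion judged on a point estimate. At an assumed SD of 5 letters the two readings fall on opposite sides of 5%, so a conservative rule could fail the criterion through measurement noise alone. The arithmetic stands. It is also true that the visible text leaves the threshold for this co-primary unstated.

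Three parts of that case are weaker than they look.

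- The silence may belong to the public copy. The visible SAP goes from 6.1.2 to 6.3, and Table 11-1 (measurement scales for ophthalmic assessments) is listed but not shown. Text withheld from the public copy cannot be treated as absent from the plan.
- Unequal counts of 2-line loss would arise anyway. The SAE definitions carry qualifiers such as haze, interface epithelium, time since surgery and exclusion of irregular astigmatism. The co-primary has none of these and is read at refractive stability, so the counts could differ even with a common 10-letter threshold.
- The size rests on two distributions that the documents do not give: the SD of change and the starting position within a line.

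**Conclusion.** The concern does not call for a change. It depends on reading a category conversion as a rule for change, which the SAP does not state. What remains is an unstated detail that an analyst would sensibly fill with a worsening of at least 10 letters (0.20 logMAR), the protocol's only stated equivalence. Were bins used instead, every loss of 10 or more letters would still count, so the departure could overstate harm but could not hide it or produce a false pass. With mean change 0 and uniform starting positions, both rules stay below 5% at SDs of 3.5 and 4 letters, and the bin count crosses 5% only above about 4.3. Those SDs are assumptions. A cross-reference to the line-loss definition in SAP 6.1.2 would be harmless but optional, and the withheld pages may already supply it.
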